4 OUTCOME MEASURES

Primary outcome measures:

The primary endpoints in sub-study 1: VISA-A at 3 and 6 months. Collected by independent evaluator via “Redcap”.

The primary endpoints in sub-study 2: VISA-A (total and pain subscales) 6 months after the 1st injection date in substudy 2. Collected by independent evaluator via “Redcap”.

The primary endpoints in sub-study 3: VISA-A score at 6 and 12 months from the day of surgery.

All patients are thoroughly instructed in visa-A score, on all visits, as it can be difficult to understand. However, it is important that they fill out the score at home directly in the assessment-

app: "Redcap" without interference of any involved investigators. Intention to treat is used so that patients who do not show up for primary outcome will have scores transferred from the last attendance.

Secondary outcome measures

Sub-study 1:

Lickert scale at 3, 6, 9 and 12 months: 11 point box scale from -5 to +5, where 0 is the status at **entry**, +5 is cured, and -5 is much worse.

VISA-A scores 1,2, 9 and 12 months, including VISA-A pain subscore during Function at all timepoints (1,2,3,6,9,12 months)

Assessment of the exercise therapy at 3 months: 11 point box scale from 0-10, where 0 is very uninspiring / boring training, and 10 is very inspiring and motivating training.

Thickness of the Achilles tendon measured by ultrasound scan, cross-sectionel image on the thickest of the tendon at 3, 6, 9 and 12 months. The thickness of the "healthy" tendon is also measured for comparison.

Ultrasound Scanning Doppler Activity assessed with Color Doppler at 3, 6, 9 and 12 months.

After 6, 9 and 12 months, it is also assessed how many percentage of previous activity level (from before the injury) they have recovered. The patient himself states this as a percentage.

Survival rate to the treatment is assessed by assessing all patients that are not satisfied with the treatment or can not comply to the training protocol.

Sub-study 2:

VISA-A score 1, 2, 3, 9 and 12 months

Thickness of the Achilles tendon measured by ultrasound scan, cross-sectional image on the thickest part of the tendon at 3,6,9,12 months. The thickness of the "healthy" tendon is also measured for comparison.

Ultrasound Scanning Doppler Activity assessed with Color Doppler at 3, 6, 9 and 12 months.

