5 SAMPLE SIZE AND POWER

Sub-study 1

The risk of finding a difference between groups, even if there really is none, is set at 5% (risk of type I error), while the risk of overlooking a difference between the groups that is actually present is set at 20% (type II error). All outcome parameters will be analyzed using Mixed Effect Analysis

Statistical Analysis Plan	Date: nov 27, 2022
Exercise/Injections/operation in Achilles midsubstance tendinopathy	
Bispebjerg Hospital	

with treatment regime (group) and time as main factor (GraphPad Prism version 9.3 for Windows, GraphPad Software, La Jolla California USA, www.graphpad.com). All analysis are performed as an intention-to-treat analysis. If a patient drops out due to no improvement or too much pain to continue exercise therapy, the missing data will still be included using the mixed effect analysis.

Q-Q plots will be visually examined prior to analysis to ensure that the assumption of normal distribution is not violated. Significance level is set to 0.05. We will also compare the “survival rate” in each training group, and compare the end result after training by performing per protocol analysis. Patients not complying at least 75% with the training protocol are not included in the per-protocol statistics.

The minimum relevant difference in VISA-A is set at 15. However, as a non-inferiority study, the difference is set to $15/2 = 7.5$. Based on other studies on pain intensity, we expect a mean baseline of 50 and an average improvement of 17. The standard deviation (SD) on the VISA-A measurements in these studies is 13. Power of 80% gives a sample size of 38 participants in each group. We plan to include 45 in each group in case of data loss and no-shows, for a total of 90 patients.

Sub-study 2:

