7.2 Statistical Analysis Plan

Statistical analysis will be undertaken using PRISM version 9.3.1. All analyses will be conducted on an intention-to-treat principle using all randomized participants in the groups they were originally randomized to. A blinded statistician will perform the data analysis. In the per-protocol analysis only patients complying at least 75% with the treatment protocol are included in the statistics.

A blinded statistician will perform the data analysis.

Demographic and anthropometric characteristics (gender, age, mass, height, body mass index, sporting activities and pain duration) will be determined at the baseline visit for each treatment group.

Statistical analyses will be conducted on all outcome measures at all timepoints. However, the primary end-point will be the total score of the VISA-A questionnaire at 3 and 6 months in substudy 1; VISA-A total score and pain-subscales at 6 months in substudy 2; and VISA-A total score at 6 and 12 months in substudy 3. Between-group comparisons of treatment effect for all primary and secondary outcomes, will be performed with a mixed effect analysis. To assess for inferiority and superiority, mean between-group differences and two-sided 95% confidence intervals will be calculated.

The ordinal scaled data of patients overall assessment of the treatment effect (Lickert score -5 to +5) will be analyzed with the same mixed effect analysis, if the data is found normally distributed.

The ordinal scaled data on satisfaction with the exercise program is analyzed with the same mixed effect analysis, if the data is found normally distributed.

The ordinal scaled data of grading the flow within the tendon into 4 categories will be calculated using non parametric statistics: Mann-Whitney U-tests.

Return to sport in percent of earlier sports activity will be compared using unpaired t-test if the data is normally distributed, otherwise non parametric analysis (Mann-Whitney) is performed.

In substudy 1 the survival rate in each exercise group is illustrated on a Kaplan-Meier plot and differences are calculated using Log rank test (Mantel-Cox test).

A two-sided P value of less than 0.05 will be considered to indicate statistical significance.

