7.4 Timing of analyses

When this statistical analysis plan was signed, recruitment to the main trial was started, but no analysis had been initiated.

SUB-STUDY 1								
	Enrolment	Allocation						
TIMEPOINT	april 2022 – end 2024	april 2022 – end 2024	Month 1	Month 2	Month 3	Month 6	Month 9 Jan 2023 end 2025	Month 12 April 2023 end 2025
ENROLMENT:								
Eligibility screen	X	X						
Informed consent		X						
Allocation		X						
INTERVENTIONS:								
Intervention group 1			←————→					
Intervention group 2			←————→					
ASSESSMENTS:								
Diagnosis		X						
VISA-A		X	X	X	X	X	X	X
Morning pain [VAS]		X	X	X	X	X	X	X
Pain after activity [VAS]		X	X	X	X	X	X	X
Return to usual sports participation						X	X	X
Satisfaction with result of treatment			X	X	X	X	X	X
Patient diary for reporting compliance and adverse events			←————→					
Ultrasound examinations		X	x	x	X	X	X	X
Demographics		X						

Table 1: SPIRIT figure. Schedule of enrolment, interventions and assessments

SUB-STUDY 2								
	Enrolment	Allocation						
TIMEPOINT	July 2022 – July 2024	July 2022 – July 2024	Month 1	Month 2	Month 3	Month 6	Month 9 Jan 2023 end 2025	Month 12 April 2023 end 2025
ENROLMENT:								
Eligibility screen	X	X						
Informed consent		X						
Allocation		X						
INTERVENTIONS:								
Exercise group 3+4			←————→					
Exercise group 5+6			←————→					
ASSESSMENTS:								
Diagnosis		X						
VISA-A		X	X	X	X	X	X	X
Morning pain [VAS]		X	X	X	X	X	X	X
Pain after activity [VAS]		X	X	X	X	X	X	X
Return to usual sports participation						X	X	X
Satisfaction with result of treatment			X	X	X	X	X	X
Patient diary for reporting compliance and adverse events			←————→					
Ultrasound examinations		X	x	x	X	X	X	X
Demographics		X						

SUB-STUDY 3					
	Enrolment	Allocation			
TIMEPOINT	End 2022 – end 2025	End 2022 – end 2025	Month 3	Month 6	Month 12 End 2023 – end 2026
ENROLMENT:					
Eligibility screen	X	X			
Informed consent		X			
Allocation		X			
INTERVENTIONS:					
operation		x			
ASSESSMENTS:					
Diagnosis		X			
VISA-A		X	X	X	X
Morning pain [VAS]		X	X	X	X
Pain after activity [VAS]		X	X	X	X
Return to usual sports participation				X	X
Satisfaction with result of treatment			X	X	X
Patient diary for reporting compliance and adverse events					
Ultrasound examinations		X	X	X	X
Demographics		X			

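### The sub-study 1 mixed model names group and time but no group-by-time term or visit contrast, so it does not define the 3- and 6-month differences declared primary and can favour non-inferiority

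*SAP*

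**What the plan says.** The model terms appear once, under Sub-study 1 in section 5: all outcome parameters go into a mixed effect analysis "with treatment regime (group) and time as main factor". Section 7.2 adds the method but no terms: "Between-group comparisons of treatment effect for all primary and secondary outcomes, will be performed with a mixed effect analysis". It then says: "To assess for inferiority and superiority, mean between-group differences and two-sided 95% confidence intervals will be calculated". No visit is attached to those differences.

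The endpoint is tied to particular visits. Section 4 has "The primary endpoints in sub-study 1: VISA-A at 3 and 6 months", and section 7.2 repeats that "the primary end-point will be the total score of the VISA-A questionnaire at 3 and 6 months in substudy 1". Section 4 lists the remaining visits as secondary ("VISA-A scores 1,2, 9 and 12 months"). The sub-study 1 schedule in section 7.4 marks VISA-A seven times ("VISA-A X X X X X X X"): at allocation and at months 1, 2, 3, 6, 9 and 12. Section 7.2 also says: "Statistical analyses will be conducted on all outcome measures at all timepoints".

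The SAP does not mention a group-by-time interaction, a visit-specific contrast, or whether the allocation score is an outcome row or a covariate. For sub-study 2, section 5 names the mixed effect analysis without giving its terms.

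**The concern.** A model with group and time as main effects has a single group coefficient. In balanced data it equals the difference between arms in patient means over all modelled visits. It is neither the month-3 nor the month-6 difference unless the treatment difference is the same at every modelled visit.

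This matters because sub-study 1 is a non-inferiority comparison with a margin of 7.5. If the allocation score is one of the outcome rows, randomisation makes the expected difference there zero, so that row pulls the estimate towards zero. In a non-inferiority test, shrinkage towards zero is the anti-conservative direction. The other secondary visits can push the estimate either way, depending on how the difference develops. As the text stands, two analysts could fit different models, report different primary results, and both claim to follow the SAP.

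**Working it through.** **Inputs from the SAP.** Margin 7.5, SD 13, 80% power, 38 per group needed and 45 per group planned (section 5, Sub-study 1); two-sided 95% confidence interval (section 7.2); seven VISA-A measurements (section 7.4 schedule).

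**Assumptions not in the SAP.** Equal correlation rho between visits, taken from 0.3 to 0.7; equal SD at each visit; complete data; the deficit profiles below. Each profile has a true app deficit of exactly 7.5 at months 3 and 6, so declaring non-inferiority is an error.

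**The plan's own figure.** n = 2 x (1.645 + 0.842)^2 x 13^2 / 7.5^2 = 37.2, rounded up to 38 per group. The stated 38 is reproduced with a one-sided 5% level. It rests on the SD at one visit and has no averaging over visits. The level used there is a separate matter; the error rates below use the 95% interval of section 7.2.

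**Standard errors at 45 per arm.**
- One visit: 13 x sqrt(2/45) = 2.74.
- Mean of seven visits: 13 x sqrt((1 + 6 rho)/7) x sqrt(2/45) = 1.73, 2.07 and 2.36 for rho = 0.3, 0.5 and 0.7.

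**False non-inferiority.** P = Phi((7.5 - averaged deficit)/SE - 1.96).

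Deficits are listed in the order allocation, months 1, 2, 3, 6, 9, 12, with allocation counted as an outcome row:

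| Profile | Averaged deficit | P at rho 0.3 / 0.5 / 0.7 |
|---|---|---|
| Constant: 0, then 7.5 six times | 45/7 = 6.43 | 9.0% / 7.5% / 6.6% |
| Builds up: 0, 2.5, 5, then 7.5 four times | 37.5/7 = 5.36 | 23.5% / 17.7% / 14.6% |
| Builds, then wanes: 0, 2.5, 5, 7.5, 7.5, 3.75, 0 | 26.25/7 = 3.75 | 58.1% / 44.0% / 35.5% |
| Larger early: 0, 15, 11, then 7.5 four times | 56/7 = 8.00 | 1.2% / 1.4% / 1.5% |

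Worked line (constant, rho 0.5): (7.5 - 6.43)/2.07 - 1.96 = -1.44, and Phi(-1.44) = 7.5%.

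**Allocation left out of the outcome rows.** The average is then over six visits, with SE = 13 x sqrt((1 + 5 rho)/6) x sqrt(2/45). The constant profile averages 7.5 and P returns to 2.5%. The build-up profile averages 37.5/6 = 6.25 and P is 10.5% to 7.6% for rho 0.3 to 0.7. Removing allocation therefore does not settle the matter when the difference varies over time.

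**Visit-specific contrast.** At month 3 or month 6 the deficit is 7.5 under every profile, so P = Phi(-1.96) = 2.5%.

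**The case against.** The strongest reply is that the SAP leaves a detail unwritten but does not choose the wrong estimand. The phrase in section 5 lists two factors; it does not say that these are the only terms, and it excludes no interaction. Section 7.2 promises analyses at every timepoint and names months 3 and 6 as primary, and section 4 separates those months from the secondary ones. Visit-specific differences are a natural reading of the intent. All of this stands.

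Three stronger readings are tempting, and the documents do not support them:
- A reader might infer that the allocation score is averaged into the treatment effect. The schedule shows only that it is collected. Without it, the constant-deficit case is back at 2.5%.
- A reader might infer that the model necessarily favours non-inferiority. A larger early deficit gives 1.2-1.5%, below nominal. A deficit that widens late (0, 7.5 four times, 10, 12.5) averages 52.5/7 = 7.5 and gives 2.5% even with allocation included.
- A reader might infer that sub-study 2 uses the same main-effects model. The wording about factors stands under Sub-study 1 and is not repeated.

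The reply does not supply a specification. An evident intent to look at months 3 and 6 does not say which model term yields those differences, and the one model that is described, fitted as written, yields neither.

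**Conclusion.** The point holds as a gap in specification with a possible effect on the primary conclusion. The only stated sub-study 1 model, taken literally, does not estimate the declared primary differences, and the SAP does not fix the interaction, the visit contrasts or the handling of the allocation score.

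The size depends on assumptions. With allocation among the outcomes, the false non-inferiority rate runs from about 1.2% to 58% across the four profiles and rho 0.3 to 0.7, against 2.5% for a contrast at the named visit. The least speculative inflated case, a constant deficit diluted only by the allocation row, gives about 7-9%. The 36-58% range needs three things together: no interaction, allocation as an outcome, and a deficit that builds and then wanes.

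Complete data is also an idealisation, since section 3 lets dissatisfied patients leave for sub-study 2 after one month. Because the non-inferiority decision against 7.5 rests on this estimate, it should be settled before the blind is broken.

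**What to change.** In section 5 (Sub-study 1) and section 7.2:
- Specify group, time as a categorical factor, and group-by-time.
- Enter the allocation VISA-A as a covariate, or constrain it to be equal between arms, and state that it is not averaged into the treatment effect.
- Define the primary estimates as the app-minus-HSR contrasts at month 3 and at month 6 from this model, each with a two-sided 95% confidence interval compared with -7.5.
- For sub-study 2, state the model terms in the same form and name the HVI-minus-CS contrast at month 6 as the estimate.

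The cost is SAP wording; section 7.4 reports that no analysis had begun at signing. The downside is a wider interval than the all-visit average: before baseline adjustment, SE about 2.7 against about 2.1 at rho 0.5. That is the single-visit precision on which the sample size was calculated.

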In cases where the above treatment measures are ineffective, surgery may be considered. Surgery of midsection AT has been tried for many years. Traditionally with longitudinal incisions of the tendon in the thickened part, but in recent years mainly as a minor intervention with a removal of the peritendium around the tendon (tenolysis) – especially on the front of the tendon, where vascular ingrowth with nerve fibers is assumed to be a large part of the cause of the pain from the tendon. Ruergård A et al (2019) have indicated a success rate of 89% with painlessness and return to sports at the same level as before the Achilles problems. In addition to this study, there are only small retrospective series of the effect of tenolysis, and in all the studies it is unclear to what extent and how effectively conservative treatment has been tried.

The purpose of our study is to compare an app based daily home training with physiotherapist supervised slow heavy strength training combined with load reduction by abstaining from running and jumping activities. This will be interesting because app based training is less costly than physiotherapeutic guided training. In addition, we will compare 50 ml of HVI with CS with 2 ml of CS injection as a supplement to training, in those patients who do not achieve satisfactory results with training alone. Finally, patients with continued problems will be offered surgery with Achilles tenolysis in an open prospective study.

The study is based on the following hypotheses:

- 1) Treatment with an app based daily home workout is as effective as slow heavy strength training (non-inferiority study).
- 2) 50 ml HVI with CS is better than 2 ml CS injection in addition to continued training, in those patients who do not achieve satisfactory results with training alone (superiority study).

- 3) Surgery with surgical tenolysis results in a clinically relevant reduction of pain symptoms in patients without sufficient effect of structured and monitored conservative treatment (the above conservative regimen).

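### Sub-study 1's 38 per group gives 80% power only at one-sided 5%, but non-inferiority will be judged with a two-sided 95% CI, so power is about 70% at 38 and 77–78% at 45

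*SAP*

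**What the plan says.** Section 1 sets the aim of sub-study 1: "Treatment with an app based daily home workout is as effective as slow heavy strength training (non-inferiority study".

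Section 5 halves the minimum relevant VISA-A difference of 15 to obtain a margin of 7.5. On variability it says: "The standard deviation (SD) on the VISA-A measurements in these studies is 13". It sets the type II error at 20% and describes the type I error as follows: "The risk of finding a difference between groups, even if there really is none, is set at 5% (risk of type I error". It adds "Significance level is set to 0.05", without saying whether that level is one- or two-sided. The result is "Power of 80% gives a sample size of 38 participants in each group", raised to 45 per group (90 in total) to allow for data loss and no-shows.

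Section 7.2 gives the rule for analysis: "To assess for inferiority and superiority, mean between-group differences and two-sided 95% confidence intervals will be calculated". It continues: "A two-sided P value of less than 0.05 will be considered to indicate statistical significance". Section 7.2 does not mention the 7.5-point margin.

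**The concern.** The sample size and the decision rule appear to use different error rates. When non-inferiority is read from a two-sided 95% interval, only one limit matters, so the test is run at one-sided 2.5%. If 38 was derived at one-sided 5%, the stated 80% power does not belong to the test that will be carried out.

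The error definition adds to this. Finding a difference when there is none is the type I error of a superiority test. For this aim, the type I error is declaring the app non-inferior when it is in truth worse by 7.5 points or more.

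Two things are at stake. First, the trial has a higher chance than stated of an inconclusive result in its main randomised comparison, even with no data loss beyond the allowance. Second, the choice between a 90% and a 95% interval can decide the conclusion. While section 5 implies one and section 7.2 states the other, that choice remains open to argument after the result is known.

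**Working it through.** **Inputs**
- Margin 7.5, SD 13, power 80%, alpha 5% with sidedness unstated: section 5.
- Allocation 1:1, 45 per group: section 3, sub-study 1 trial design, and section 5.
- Two-sided 95% CI: section 7.2.
- True difference 0: an assumption. Section 5 gives a single expected improvement of 17, with no separate value by arm.

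**Formula for n per group**

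n = 2 × (SD / margin)² × (z₁₋α + z₀.₈₀)², where 2 × (13 / 7.5)² = 6.009.

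**Reproducing the SAP's figure (one-sided 5%)**

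6.009 × (1.645 + 0.842)² = 37.15, so **38**. The noncentral t also gives 38, with power 80.1%. This matches the SAP exactly.

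**Under the section 7.2 rule (two-sided 95% CI, one-sided 2.5%)**

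6.009 × (1.960 + 0.842)² = 47.16, so **48**. The noncentral t gives 49 (power 79.9% at 48 and 80.7% at 49).

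**Other readings tried**
- Difference of 15: 12 per group two-sided, 10 one-sided.
- Two one-sided tests for equivalence: 51.46, so 52 per group.

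Neither gives 38.

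**Power at the SAP's numbers**

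Normal approximation: power = Φ(7.5 / (13 × √(2/n)) − z₁₋α).
- n = 38 at one-sided 2.5%: 7.5 / 2.982 = 2.515, and Φ(2.515 − 1.960) = 71.0%.
- n = 45 at one-sided 2.5%: 7.5 / 2.741 = 2.737, and Φ(2.737 − 1.960) = 78.1%.

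| n per group | One-sided 5%: normal / t | One-sided 2.5%: normal / t |
|---|---|---|
| 38 | 80.8% / 80.1% | 71.0% / 69.9% |
| 45 | 86.2% / 85.8% | 78.1% / 77.2% |
| 48 | 88.1% / 87.7% | 80.7% / 79.9% |
| 49 | 88.7% / 88.3% | 81.5% / 80.7% |

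**Allowance for loss**

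Raising 38 to 45 implies a loss of 1 − 38/45 = 15.6%. At that loss, 48 evaluable needs 48 × 45/38 = 56.8, so 57 per group. For 49 it is 58.03, so 59 per group. The total is 114 to 118.

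**Comparison with the other sub-studies**

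Sub-study 2's 22 patients, read as per compared group and with SD 13 assumed (that paragraph gives none), reproduces at two-sided 5%: 2 × (13/11)² × (1.960 + 0.842)² = 21.9. One-sided 5% would give 18. Sub-study 3's 8 patients have 79.9% power with a two-sided 5% paired t-test and 90.0% with a one-sided one. Only sub-study 1 rests on an undeclared one-sided 5%.

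**The case against.** Several points on the other side are fair.

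- **The shortfall at 45 is small.** It is 1.9 points (normal) or 2.8 points (t), which is minor beside the uncertainty in an SD taken from other studies. All randomised patients are to stay in the mixed-effect analysis. This stands as far as it goes. However, the extra 7 per group are there to cover loss, so 45 evaluable is the best case, and the SAP attaches its 80% to 38, where the gap is 9 to 10 points.
- **The 95% interval is the stricter rule.** It does not raise the risk of a false claim of non-inferiority. That is correct; the harm is lost power and a rule that can be disputed.
- **One-sided 5% can be a legitimate choice.** It can, but the SAP does not make it. The one-sided 5% is inferred from the number 38, and section 7.2 states the opposite.
- **The mixed model may recover precision.** It may, under conditions. If 13 is the SD of raw scores, adjustment for baseline restores 80% when the baseline–outcome correlation is at least about 0.21 (45 per group) or 0.44 (38 per group). If 13 is the SD of change, the gain exists at 45 per group for correlations below about 0.91. Section 5 names only group and time as main factors, gives no correlation and claims no such gain, so this cannot support the 80% as written.
- **The type I wording changes no number.** True, but it describes a different test from the one planned.

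**Conclusion.** The concern holds. The 38 per group is correct arithmetic for a one-sided 5% test, and the SAP specifies no such test. Under the two-sided 95% interval of section 7.2, power is 70–71% at 38 evaluable per group and 77–78% if all 45 are evaluable. The stated power would need 48 to 49 evaluable per group. For a truly equivalent app, the chance of failing to show non-inferiority at 38 per group is about 29–30%, not 20%.

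The gap at 38 is the substantial part; the gap at 45 is real but small. The figures rest on the SAP's margin and SD, a true difference of zero, no covariate adjustment, and one comparison at a single time point.

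**What to change.** In section 5, for sub-study 1:

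1. State that non-inferiority is concluded if the lower limit of the two-sided 95% CI for app minus HSR (higher VISA-A taken as better) lies above −7.5, and that this is one-sided alpha 0.025. Repeat the margin in section 7.2.
2. Restate the power without covariate adjustment as about 70% at 38 evaluable per group and 77–78% at 45.
3. Redefine type I error as declaring the app non-inferior when it is truly worse by 7.5 or more, and type II error as failing to declare non-inferiority when the arms are truly equal.
4. If baseline adjustment is to be relied on to bring power back towards 80%, write the baseline term into the model and state the correlation assumed.

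This costs wording only and needs no further patients; the price is a less favourable stated power. Section 7.4 records that recruitment was under way but no analysis had begun at signing, so the change should be dated before unblinding.

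Two alternatives would also make the sections agree. One is to declare and justify a one-sided 5% test with a 90% CI in section 7.2. The other is to keep 80% power at the 95% level by recruiting 57 to 59 per group at the SAP's implied loss. The first relaxes the stated decision rule after recruitment has started, and the second adds 24 to 28 patients to the planned 90.

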Substudy 1 is an evaluator blinded randomized controlled trial with follow-up after 3, 6, 9 and 12 months. Patients not satisfied with the outcome in substudy 1 after at least 1 month of training, have the possibility to drop-out of this substudy and be included in substudy 2. Drop-outs are recorded as “non-survivors” and a "Survival" curve is recorded for each exercise group. A total of 90 patients are included, 45 patients in each of the 2 training groups. All patients will be included in the intention to treat analysis, but we will also perform a per-protocol analysis only including patients performing at least 75% of the training programs.

Anyone who ceases due to unsatisfactory effect in sub-study 1 can be included in the second part of the study after at least 1 months of training and no later than after 12 months.

Sub-study 2

Single blinded (assessor and statistics) Randomized Controlled Trial.

Randomization method

Randomization must be preceded by informed consent and power of attorney. The randomization of patients is performed by an independent office employee not involved in patient care ([name]) using a computer generated randomization schedule (MINIMPY, Maghaei 2010) using permuted block sizes (two to four). The employee is blinded to the block sizes. The allocation of each patient is stored in a computer drive with exclusive access only for the responsible office employee ([name]). Patients will be divided equally into 4 groups. No further stratification will be carried out in part 2 of the study.

The secretary is then in charge of filling out randomization sheets and preparing the CRF (clinical research files).

Blinding

The study will be evaluated blinded. The doctors who give the injections cannot be blinded due to the large difference in the injection volume. Patients cannot be blinded to the training performed and can probably feel whether a small or large volume is being injected. The effect of the training is evaluated monthly by the patient himself at home without interference with any investigators on an app (Redcap). At every doctors appointment US assessment of the Achilles tendon will be performed.

The 4 secondary treatment arms

Patients continue in the allocated training (Heavy Slow Resistance exercise or App guided training) and treatment is supplemented with either corticosteroid injection (CS) or High Volume Injection (HVI). This results in 4 groups:

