In a previous study, 25% achieved satisfactory effect from training alone. If the same is seen in the current study, approximately 67 will want additional treatment. Of these, we expect that 50 will continue in sub-study 2. Sub-study 2 is a superiority study, and 22 patients are needed to have an 80% chance of finding, with 5% significance level, a difference in VISA-A scores of more than 11 between treatment groups using Mixed Effect Analysis using the intention to treat principle. Patients are divided into 4 groups, but this sub study will be powered to detect differences between exercise therapy+HVI and Exercise therapy +CS injection. This means that the combination of group 3 and group 5 are compared to the combination of group 4 and group 6. However, we will also compare group 3 to group 4, and group 5 to group 6.

Q-Q plots will be visually examined to ensure that the assumption of normal distribution is not violated prior to analysis.

Sub-study 3

	Statistical Analysis Plan	Date: nov 27, 2022
Bispebjerg Hospital	Exercise/Injections/operation in Achilles midsubstance tendinopathy	

is a prospective quality assurance study. Paired T-test is used for calculating differences from before operation to 3, 6 and 12 months after operation. Change in VISA-A score is the primary outcome at 6 and 12 months, with an expected preoperative score of 50 and a relevant improvement is set to 15. The standard deviation of the difference is from earlier studies 13. In order to record an improvement of at least 15 points with a risk of type I error of 5% and type II error of 20%, 8 patients would have to be included in this study.

Data processing:

Entry data is registered in Redcap, where all information from each individual subject is collected.

Each patient is assigned an anonymous unidentifiable project number: Ach2019-n.

Project numbers are listed on all CRF and patient diaries.

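### Sub-study 1 allows for 16% loss, but the SAP itself forecasts that 56% of patients will move to sub-study 2; the two are not reconciled, so 80% power at month 6 is not supported

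*SAP*

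**What the plan says.** For sub-study 1, section 5 of the SAP sets a non-inferiority margin of 7.5 VISA-A points, an SD of 13 and a 5% type I error without saying whether it is one- or two-sided. It concludes: "Power of 80% gives a sample size of 38 participants in each group". It then adds a reserve: "We plan to include 45 in each group in case of data loss and no-shows, for a total of 90 patients".

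For sub-study 2, the same section applies a 25% success rate for training alone, so that about 67 of the 90 would want more treatment. It continues: "Of these, we expect that 50 will continue in sub-study 2".

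Under the sub-study 1 trial design in section 3, patients dissatisfied after at least one month of training "have the possibility to drop-out of this substudy and be included in substudy 2". They may enter sub-study 2 up to month 12 and are recorded as non-survivors of sub-study 1.

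Section 4 fixes the time points: "The primary endpoints in sub-study 1: VISA-A at 3 and 6 months". It also says that patients absent at the primary outcome have their last score carried over. Sections 5 and 7.1 instead keep drop-outs in through the mixed effect analysis, and section 5 calls their later data missing. On the decision rule, section 7.2 says: "To assess for inferiority and superiority, mean between-group differences and two-sided 95% confidence intervals will be calculated".

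**The concern.** The reserve of 7 per arm is described only as cover for ordinary data loss and no-shows. The design creates a second and larger source of loss: on the SAP's own forecast more than half of the randomised patients will at some point leave sub-study 1, and leaving is possible before both primary time points. Nothing in section 5 connects this forecast to the reserve or to the 80% figure.

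At stake is how much information the 6-month comparison will carry. Fewer observed scores mean a wider interval and a lower chance of excluding a 7.5-point deficit when the two programmes are truly equal. The exits are also informative, since patients leave because training has not worked, so the handling of their scores can affect bias as well as precision.

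**Working it through.** **Inputs from the SAP.** Margin 7.5, SD 13, power 80%, 38 needed and 45 planned per arm, and 50 of 90 expected to move (section 5); moves allowed from month 1 to month 12 (section 3); primary time points at months 3 and 6 (section 4).

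**Assumptions.** True difference 0; exits split evenly, 25 per arm; no ordinary loss on top. The share of movers gone by month 6, *f*, is not given and is varied from 0 to 1.

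**Reproducing the SAP's figure.** n per arm = 2·SD²·(z₁₋α + z₀.₈₀)² / margin².

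- One-sided 5%: 2 × 169 × (1.645 + 0.842)² / 56.25 = 37.2, rounded up to 38. This reproduces the SAP.
- One-sided 2.5%, which a two-sided 95% interval implies: 2 × 169 × (1.960 + 0.842)² / 56.25 = 47.2, rounded up to 48. This does not.

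**Allowance against forecast.** Allowance: (45 − 38)/45 = 7/45 = 15.6%. Forecast movers: 50/90 = 55.6%. The reserve absorbs 2 × 7 = 14 movers before the observed number falls below 38 per arm, which is 14/50 = 28% of those forecast.

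**Power from observed patients only.** n = 45 − 25*f*; SE = 13·√(2/n); power from the non-central t with 2n − 2 degrees of freedom and non-centrality 7.5/SE.

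| Movers gone by month 6 | Observed per arm | SE | Power, one-sided 5% | Power, two-sided 95% CI |
|---|---|---|---|---|
| 0 | 45 | 2.74 | 86% | 77% |
| 14 (28%) | 38 | 2.98 | 80% | 70% |
| 25 (50%) | 32.5 | 3.22 | 74% | 63% |
| 50 (100%) | 20 | 4.11 | 56% | 43% |

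**Recovery by a mixed model.** Suppose that each mover contributes one earlier score with correlation ρ to month 6 (ρ is an assumption; the SAP gives none). The effective number per arm is 1 / [(1 − ρ²)/n + ρ²/45]. Power at one-sided 5%, by normal approximation:

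| | ρ = 0.5 | ρ = 0.7 | ρ = 0.9 |
|---|---|---|---|
| Half gone: effective n | 34.9 | 37.6 | 41.9 |
| Half gone: power | 78% | 80% | 84% |
| All gone: effective n | 23.2 | 27.5 | 36.4 |
| All gone: power | 63% | 69% | 79% |

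The normal approximation runs about one point above the t-based figures; on the same basis the observed-only values are 75% (half gone) and 57% (all gone).

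**The case against.** The strongest reply has four parts.

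*Timing.* The 55.6% is total movement over months 1 to 12, not loss at month 6. A reader might infer that 56% of month-6 scores will be absent, and that 80% power therefore fails or that 86 per arm (38/(1 − 0.556)) must be recruited. The SAP does not support that: it gives no timing, and on the basis that yields 38 the 80% survives if no more than 14 of the 50 leave before month 6. This part stands. The limit of 14 does, however, spend the whole reserve on movers and leaves nothing for the ordinary loss it was meant to cover.

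*Movers are not simply deleted.* A mixed model uses their earlier scores and may recover a good deal: with half gone, power is back near 80% at a correlation of 0.7. This also stands, but recovery is partial and depends on a correlation that the SAP does not state. Under the carry-forward rule of section 4 the nominal number stays at 45, and the problem becomes bias. Scores frozen at the point of leaving for lack of effect can pull the arms together, which favours non-inferiority.

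*Sidedness.* It is tempting to quote 63% or 43% as the cost of exits. Those figures rest on the two-sided 95% interval, under which power is already 77% at 45 per arm with nobody gone. That first shortfall arises from sizing at one-sided 5% and analysing at 2.5%; it is a separate matter and is not caused by movers.

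*Month 3.* It is also a primary time point, and no more movers can have left by then than by month 6, so the loss there is no larger.

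Nor is there an arithmetic error in the 38, which reproduces exactly.

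**Conclusion.** The point holds as an unreconciled planning assumption. The SAP allows for 15.6% loss and forecasts 55.6% movement out of the same sub-study without relating the two, so its 80% power at month 6 is not supported. On the SAP's implied one-sided 5% basis the plausible range from observed patients alone is 86% down to 56%, depending on how many of the 50 have left by month 6. A mixed model lifts the half-gone and all-gone cases to about 78–84% and 63–79% for correlations of 0.5 to 0.9. These figures assume no true difference, an even split of exits and no other loss. The documents do not support the flat statement that power fails. The conflict between carry-forward in section 4 and the mixed model in sections 5 and 7.1 also has to be settled, since it decides whether the main consequence is lost precision or bias.

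**What to change.** 1. State in sections 4 and 5 that VISA-A continues to be collected in REDCap at months 3 and 6 on the sub-study 1 clock for every randomised patient, including those who enter sub-study 2. Section 3 already has these patients reporting monthly in REDCap, so the burden is small. Scores not collected cannot be recovered later.
2. Use the mixed model without carry-forward, and amend section 4 to agree with sections 5 and 7.1. State whether scores after an injection enter the primary non-inferiority analysis, and give the other handling as a sensitivity analysis. This matters because movers in both arms receive injections, so injected scores, like frozen ones, can draw the arms together and favour non-inferiority.
3. Replace the single 80% figure with power at month 3 and at month 6 under a stated share of the 50 forecast movers gone by each time point, and name the significance level used.

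The cost is SAP wording and two REDCap time points kept on the original schedule. The stated power will look less favourable; no extra patients are needed.
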